6.3.1. Main Analysis

Change in Mayo score (complete, [REDACTED] from Baseline to Week 10 will be analyzed using an analysis of covariance (ANCOVA) model adjusted for corticosteroid use at screening (yes or no), prior anti-TNF use (yes or no), and the Baseline Mayo score, using observed cases. Actual values and changes from Baseline will be descriptively summarized. The adjusted least-squares means and standard errors (SEs) with 95% CI for the difference in mean changes from Baseline and p-values will be reported. The Week 5 visit, when applicable, will also be included in the same table. For example, there will be an analysis for partial Mayo score at Week 5 but not for complete or 9-point Mayo scores.

Proportion of adult patients with histologic remission at Week 10 will each be analyzed and reported using the same stratified CMH test as specified for the primary analysis of the primary endpoint in Section 6.1.1, using NRI described in Appendix 1.3, including a bar graph showing the percentages by treatment/cohort with the weighted treatment difference, associated 95% CI and CMH p-value. [REDACTED]

Proportion of adult patients with clinical response, remission, or endoscopic improvement at Week 10 in patients who previously received anti-TNF therapy will be analyzed and reported using the same stratified CMH test as specified for the primary analysis of the primary endpoint in Section 6.1.1, except prior anti-TNF use stratification factor will not be used, using NRI described in Appendix 1.3.

[REDACTED]

[REDACTED]

[REDACTED]

[REDACTED]

[REDACTED]

[REDACTED]

[REDACTED]

[REDACTED]

[REDACTED]

[REDACTED]

[REDACTED]

[REDACTED]

[REDACTED]

[REDACTED]

[REDACTED]

[REDACTED]

6.4. Subgroup Analysis

Subgroup analyses will be performed for the endpoints of clinical remission and clinical response only using the three-component Mayo score based on a 7-day scoring algorithm ([Appendix 3.2](#)). For each specific subgroup, if there are not enough patients (i.e., <5% ITT population), the corresponding analyses will not be performed. The following are the pre-defined subgroups:

1. Corticosteroid use at screening (yes vs. no)
2. Prior anti-TNF use (yes vs. no)
3. Baseline complete Mayo score (≤ 9 vs. > 9)
4. Extent of colitis (left-sided vs. extensive)
5. Sex (female vs. male)
6. Age at screening (\leq median vs. $>$ median)
7. Baseline fecal calprotectin (≤ 250 vs. > 250 mg/kg)
8. Baseline ALC ($\leq 1,500$ vs. $> 1,500$ $10^6/L$)
9. Years since initial UC diagnosis (≤ 4 vs. > 4 years)
10. Region (North America, Eastern Europe, Western Europe, Asia Pacific)
11. Baseline partial Mayo score (\leq median vs. $>$ median)

12. Baseline partial Mayo score (≤ 7 vs. >7)

13. Baseline endoscopy subscore (2 vs. 3)

Other subgroups such as race (white vs. non-white), weight (\leq median vs. $>$ median), 5-aminosalicylic acid (5-ASA) use at screening (yes vs. no), and corticosteroid and 5-ASA use at screening (yes vs. no), and moderate UC at screening may also be explored.

[REDACTED]

[REDACTED]

[REDACTED]

[REDACTED]

- [REDACTED]

- [REDACTED]

- [REDACTED]

[REDACTED]

[REDACTED]

[REDACTED]

[REDACTED]

[REDACTED]

[REDACTED]

[REDACTED]

[REDACTED]

- [REDACTED]

- [REDACTED]

[REDACTED]

[REDACTED]

[REDACTED]

- [REDACTED]
- [REDACTED]
- [REDACTED]

[REDACTED]

[REDACTED]

- [REDACTED]
- [REDACTED]

[REDACTED]

6.7. Result Blinding

Before unblinding Cohort 1 treatment codes, results of PK, total and differential white blood cell (WBC) count (basophils, eosinophils, lymphocytes, monocytes, and neutrophils), fecal calprotectin, and C-reactive protein beyond first dose will not be disclosed to preserve the blind.

6.8. Interim Analysis

No interim analyses for efficacy are planned during the conduct of the IP.
The data from the IP in Cohort 1 will be cleaned, unblinded, and analyzed after the last Cohort 1 patient has had their last IP visit (I 3 Visit). The analysis of Cohort 1 induction data which is

used for planning for future development will be carried out by designated un-blinded Biostatistics and Programming teams at PPD (a CRO), the same teams already contracted to support the on-going DSMB meetings for this study. A limited number of Sponsor (i.e., Celgene) members who are not part of the study team will have access to the Cohort 1 induction analysis results. The review and conduct of the study will continue in a blinded manner by study team members that are blinded to all study data until all randomized subjects have completed 42 weeks of the Maintenance Phase (Week 52 of overall study duration). The process the Cohort 1 induction analysis will be documented in a charter in a separate document.

The data from Cohort 2 will be cleaned, locked, and analyzed after the last Cohort 2 patient has had their last Cohort 2 visit. The treatment blind for the Maintenance Period will not be broken until the end of the study.

An independent data safety monitoring board (DSMB) will be charged with monitoring accumulating safety data from the trial, as well as general aspects of trial conduct.

The committee will meet periodically during the trial (approximately 4 times each year) to review aggregate analyses by treatment group concerning enrollment, treatment compliance, adherence to follow-up schedule, and safety data from the trial. The DSMB may recommend modifying or stopping the trial early due to safety concerns based on data reviews. The unblinded data will be prepared by an independent team at the CROs.

The blinding plan to assure that all personnel involved in the conduct of the trial remain blinded to the results of interim reviews will be specified in the DSMB Charter.

7. SUMMARY OF PATIENT DISPOSITION

The disposition of patients will be summarized with numbers and percentages by treatment/cohort and in Total Cohort 1 for all randomized subjects (Cohort 1) and all enrolled subjects (Cohort 2). Summaries will include the number and percentage of patients in the following

- Never dosed, Dosed, Completed the IP, and Discontinued from the IP.
- Primary reasons for discontinuation from the IP.

Patients who were randomized to Cohort 1 or enrolled to Cohort 2 will be summarized with number and percentage by region, country, and site for all randomized subjects (Cohort 1) and all enrolled subjects (Cohort 2). Patients who were dosed and who completed the induction period will be summarized with number and percentage by region, country, and site for the ITT population.

Patients in each analysis population as defined in Section 5 will be summarized with number and percentage.

Patients who were screened and who failed screening will be summarized with number and percentage by reason for All Consented population.

Patient disposition will be listed for the ITT population. Patient eligibility will be listed for All Consented population.

8. DEMOGRAPHICS AND BASELINE CHARACTERISTICS

Summaries for the demographics, baseline characteristics, medical history, prior medication, and protocol deviations will be presented for the ITT population by treatment/cohort and in Total Cohort 1 unless specified otherwise. Concomitant medications will be presented for the Safety population by treatment/cohort and in Total RPC1063 1 mg. Individual listings will also be provided, including concomitant medical procedures for the Safety population.

8.1. Demographics

Demographic characteristics including age, age category (18-29, 30-39, 40-49, 50-59, 60-69, 70-75, < 65, ≥ 65, ≤ Cohort 1 median, and > Cohort 1 median), sex, race, ethnicity, weight, height, body mass index (BMI), region (North America, Eastern Europe, Western Europe, Asia Pacific, South America, South Africa), country, and tobacco/nicotine usage (never, former, current) will be summarized for the ITT population and the PP population. Demographic characteristics will also be summarized for All Screen Failures, except weight, height, and BMI, which are not collected for screen failure patients. See reporting convention in [Appendix 1.1](#).

8.2. Ulcerative Colitis Disease Characteristics at Baseline

Ulcerative colitis disease characteristics at baseline including corticosteroid use at screening and prior anti-TNF use as entered in IXRS, actual corticosteroid use at screening and prior anti-TNF use as derived by concomitant medication and prior UC medication eCRFs (corticosteroid and TNF-alpha antagonist, respectively), prior corticosteroid use, prior immunomodulator use, prior biologics use except TNF-alpha antagonist, and prior oral 5-ASA use will be summarized for the ITT population and the PP population. See reporting convention in [Appendix 1.1](#).

The following UC disease history parameters will be summarized in the same table.

- Age at UC symptom onset
- Age at UC diagnosis
- Years since UC symptom onset
- Years since UC diagnosis
- Years since UC diagnosis category (0 to <1, 1 to <2, 2 to <5, 5 to <10, 10 to <15, ≥15, ≤4, >4)
- Extent of colitis (left-sided vs. extensive)
- Complete Mayo score at Baseline using the central endoscopy subscore

- Complete Mayo score at Baseline category using the central endoscopy subscore (≤ 9 vs. > 9)

█ [REDACTED]

█ [REDACTED]

█ [REDACTED]

█ [REDACTED]

█ [REDACTED]

█ [REDACTED]

8.3. Medical History

A summary of medical history, excluding data collected on the UC history and disease status eCRF, will be presented by system organ class (SOC) and preferred term (PT) according to the Medical Dictionary for Regulatory Affairs (MedDRA) version 18.1, or higher, using number and percentage of patients.

[figure not shown]
█ [REDACTED]

█ [REDACTED]

█ [REDACTED]

█ [REDACTED]

█ [REDACTED]

9. STUDY TREATMENTS AND EXTENT OF EXPOSURE

All patients will initiate investigational drug via a 7 day dose escalation regimen starting with RPC1063/ozanimod HCl 0.25 mg (equivalent to ozanimod 0.23 mg) or matching placebo (matching placebo for Cohort 1 only) on Days 1 to 4 and RPC1063/ozanimod HCl 0.5 mg (equivalent to ozanimod 0.46 mg) once daily or matching placebo on Days 5 to 7. On Day 8, patients will receive the final dose level (1 mg once daily or matching placebo) for 9 weeks. Patients will record whether they took the daily dose of medication in a diary that will be reviewed periodically by site staff and the Site Monitor.

There will be an individual investigational drug accountability record for each patient and the Investigator should maintain accurate records of the disposition of all investigational drug supplies received during the trial. The number of capsules and date investigational drug supplies are dispensed to the patient and returned by the patient are reported on the Drug Log eCRFs. Overdoses are reported on the Overdose Log eCRF and drug interruptions are reported on the Drug Interruption Log eCRF.

A summary of extent of exposure to IP treatment for the Safety population will include overall treatment duration, dose modifications, and treatment compliance, as defined in Section 9.1, Section 9.2, and Section 9.3. The summary will be presented by treatment/cohort and in Total RPC1063 1 mg. Individual data listings will also be provided.

9.1. Treatment Duration

Additional investigational drug may be dispensed to patients at Week 10 visit (I3) who will continue with maintenance period but could not complete the first maintenance visit (M1) on the same day as I3. To account for this possibility of extended IP treatment, overall IP treatment duration (TDUR_IP) will be defined as:

- the total number of days from the date of first dose to the date of last dose as reported on the End of Study eCRF for patients who do not enter MP, or
- the total number of days from the date of first dose to the date before onsite dosing for MP for patients who enter MP.

If the date of last IP dose is incomplete, see imputation method in [Appendix 2](#) before calculating treatment duration. Overall IP treatment duration will be summarized descriptively.

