- ^c In general, for patients completing the IP and entering the MP, Visit 3 of the IP (Visit I 3) will serve as Visit 1 of the MP (Visit M 1). Patients should enter the MP within 21 days of the Visit I 3 endoscopy. Procedures completed during Visit I 3 do not need to be repeated if Visit M 1 occurs within 14 days of I 3 visit. Patients may complete the M 1 visit prior to completing the OCT and PFT scheduled for the I 3 visit. OCT and PFT must be completed within 14 days of the I 3 visit.
- ^d Medical history will include smoking history. The Visit I 1 medical history can be abbreviated, noting events that occurred between Screening and Visit I 1.
- ^e TB must be ruled out according to local medical practices, such as a TB skin test, QuantiFERON Gold test, or other interferon gamma release assay (eg, T-SPOT). Subjects with a positive test result using a TB skin test or QuantiFERON Gold test must have documentation of completed TB treatment by local standard of care.
- ^f Serology testing will be performed at Screening to determine the patient's immune status with respect to the following viruses (see [Section 12.1.11](#)): Human immunodeficiency virus antibodies, anti-hepatitis A virus IgM, hepatitis B surface antigen, anti-hepatitis B core antigen, hepatitis B DNA, anti-hepatitis C virus IgG or IgM. In addition, patients must have documentation of positive Varicella Zoster Virus IgG antibody status or complete Varicella Zoster Virus vaccination at least 30 days prior to first dose of investigational drug.
- ^g At Screening, the stool sample should be used to rule out serious infection and should include evaluation for *C. difficile* toxin as well as ova and parasitic examination.
- ^h Investigational drug will only be dispensed for patients that could not complete the M1 Visit on the same day as the I 3 Visit.
- ⁱ For females of childbearing potential only, a serum β -hCG pregnancy test at Screening is required and a urine β -hCG pregnancy test is required at each visit. Between scheduled visits up until the 90-day Safety Follow-up Visit, monthly home urine pregnancy tests should be performed by the patient. If a urine pregnancy test result is positive, the investigator will instruct the patient to suspend further study dosing, if applicable, and schedule a follow-up appointment as soon as possible. A serum pregnancy test will be performed for confirmation, including after the 90-day Safety Follow-up Visit, if needed.

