9.2.2. Maintenance Period

Patients from Cohort 1, Cohort 2 [REDACTED] who complete the IP and are in clinical response at Week 10 will be eligible to enter the randomized, double-blind, placebo-controlled MP. Patients who received RPC1063 and showed a clinical response during the IP (Cohort 1, Cohort 2 [REDACTED] will be randomized to receive either RPC1063 1 mg or placebo in a 1:1 ratio. Patients randomized to placebo in Cohort 1(adults) [REDACTED] who demonstrate a clinical response during the IP will continue to receive placebo in the MP in a double-blind manner. [REDACTED]

In general, for patients completing the IP and entering the MP, Visit I3 of the IP will serve as Visit M 1 of the MP. Procedures completed during IP Visit I 3 (Week 10) do not need to be repeated if the MP Visit M 1 occurs within 14 days of the I 3 visit. Patients should enter the MP within 21 days of the Visit I 3 endoscopy.

Patients randomized into the MP will be stratified by clinical remission status at Week 10 (yes or no) and corticosteroids use at Week 10 (yes or no).

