5.2. Per-Protocol (PP) Population

The PP population will consist of all patients in the ITT population who adhered to the protocol with no major protocol deviation that potentially affects efficacy in the induction period. This population will be used in the sensitivity analysis of clinical remission and additional analysis of clinical response to evaluate the influence of major protocol violators and protocol deviators on the primary results. Patients will be excluded from this population if they meet any of the following reasons, which will be documented prior to database snapshot:

- Investigational drug noncompliance > 20% (i.e., overall IP drug compliance not in [80%, 120%])
- Receiving incorrect investigational drug leading to a treatment change for more than 1 week in the IP
- Prolonged concomitant use of systemic corticosteroids (except topical use) > 7 days before Week 10, for treatment of disease other than UC, at a total daily dose higher than the maximum dose taken between the Screening and Baseline

- Concomitant use of protocol-specified excluded medication that potentially affects efficacy for unrelated comorbid condition

█ [REDACTED]

- Violation of key entry criteria (i.e., inclusion criterion #4 [Have active UC defined as Mayo score of 6 to 12 inclusive, with endoscopic subscore of ≥ 2 , a rectal bleeding score of ≥ 1 , and a stool frequency score ≥ 1], exclusion criterion #2 [Diagnosis of Crohn's disease or indeterminate colitis or the presence or history of a fistula consistent with Crohn's disease or microscopic colitis or radiation colitis or ischemic colitis], and primary non-responders to 2 or more biologic agents approved for the treatment of UC)

The PP population will be fully identified and documented prior to induction treatment is unblinded. Patients excluded from PP population and the reason for exclusion will be listed. Similar to the ITT population, PP patients in Cohort 1 who received an incorrect investigational drug from that which was randomized will be summarized in the treatment group according to the intended randomization. Patients in Cohort 1 who were randomized with a misreported stratum will be analyzed according to their original [misreported] stratum.

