9.3. Treatment Compliance

Treatment compliance for IP will be calculated for each patient by taking into account whether a patient takes all doses of investigational drug as instructed.

For subjects undergoing dose escalation, the total number of capsules expected to be taken by a patient is calculated as follows:

Last dose date – first dose date + 4 (+ 1 to account for the number of days between those dates inclusive and +3 to account for 3 extra capsules taken during dose escalation on Study Days 5-7)

If a patient discontinues trial during or prior to Study Days 5-7 during which 2 capsules per day are taken, then the number of capsules expected will be adjusted accordingly. For example, if discontinuing on Day 5, then +1; on Day 6, then +2; on Day 7 or after, then +3.

The total number of IP capsules actually taken by a patient is defined as the total number of capsules dispensed – total number of capsules returned during IP, as reported on the Drug Log eCRFs. The overall IP treatment compliance (%) will be calculated as the total number of IP capsules taken divided by the total number of IP capsules expected and multiplied by 100. If the bottle is not returned by the patient at a visit, then the subject is considered to have returned zero pill from the unreturned bottle in the treatment compliance calculation.

The total number of IP capsules expected, actually taken and overall IP treatment compliance will be calculated and summarized after taking into account all such visits at which the bottle is not returned.

Additionally, the number and percentage of patients will be summarized by category (<50%, 50% to <60%, 60% to <70%, 70% to <80%, 80% to 100%, and >100%). Two additional categories (<80% and >120%) will also be included.

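### The compliance figure that decides Per-Protocol membership has no Week 10 cut-off, so dosing after the outcome visit can move Week 10 responders, and only responders, out of or back into the Week 10 Per-Protocol analyses

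*SAP*

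**What the plan says.** - **PP criterion.** SAP 5.2 lists, among reasons for which patients will be excluded, "Investigational drug noncompliance > 20% (i.e., overall IP drug compliance not in [80%, 120" (the interval closes at 120%). On the use of the set it says: "This population will be used in the sensitivity analysis of clinical remission and additional analysis of clinical response".
- **Compliance formula.** SAP 9.3 takes expected capsules as "Last dose date – first dose date + 4". Capsules taken are those dispensed minus the "total number of capsules returned during IP, as reported on the Drug Log eCRFs". A bottle that is not returned counts as fully taken. The section states no Week 10 cut-off, does not define the last dose date, and does not refer to SAP 9.1.
- **Bridging supply.** SAP 9.1 says: "Additional investigational drug may be dispensed to patients at Week 10 visit (I3) who will continue with maintenance period", where M 1 cannot be done on the same day. It calls this extended Induction treatment and sets the duration for Maintenance entrants as "the total number of days from the date of first dose to the date before onsite dosing for MP for patients who enter MP". Protocol Table 1, footnote h, agrees on who receives it: "Investigational drug will only be dispensed for patients that could not complete the M1 Visit on the same day as the I 3 Visit".
- **Timing.** Protocol 9.2.2 says that I 3 generally serves as M 1, and otherwise: "Patients should enter the MP within 21 days of the Visit I 3 endoscopy". Table 1, footnote m, lets that endoscopy precede I 3 by up to 10 days.
- **Who can enter Maintenance.** Only patients in clinical response at Week 10, by either Mayo definition (Protocol 7.1; SAP 4.1). Cohort 1 placebo responders also continue, on placebo.

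**The concern.** The PP analyses are meant to show how far protocol deviations influence the Week 10 result. A criterion for that purpose should depend on what happened up to the Week 10 assessment. Here, when the two visits are split, it can also depend on what the patient did with drug handed out at the outcome visit. That supply goes only to patients continuing to Maintenance, who have to be responders. Non-responders have no such window.

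PP membership can then depend on events after the outcome in a group defined by the outcome. The active arm is expected to have more responders, so more of its patients are exposed to the rule. SAP 10 says that exclusion decisions are made without knowledge of treatment. It does not say they are made without knowledge of the Week 10 outcome.

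**Working it through.** **1. Reproduce the SAP formula.** With I 3 on Day 70, the dosing schedule gives 4×1 + 3×2 + 63×1 = 73 capsules. SAP 9.3 gives (70 − 1) + 4 = 73. They also agree on Day 60 (63) and Day 80 (83), the ends of the I 3 window.

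**2. Longest gap.** Let g be the number of days after I 3 and before M 1 dosing. M 1 is due within 21 days of the endoscopy, which falls 0 to 10 days before I 3. So g is at most 20 minus the endoscopy lead time.

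**3. General expression.** With T capsules taken by Day 70 and k taken in the gap, compliance = (T + k)/(73 + g), where g runs to whichever date is read as the last Induction dose.

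**4. Narrow reading.** Last dose date is the last Induction capsule actually taken, and the M 1 return counts as Induction.
- Out: T = 62 (84.9%); only the last of 10 gap doses is taken: 63/83 = 75.9%.
- In: T = 58 (79.5%); two gap doses taken: 60/75 = 80.0%, inside the closed interval. T = 57 (78.1%) passes after 7 gap doses: 64/80 = 80.0%.
- A fully compliant patient is lost only at the extreme: one dose, on the last of 20 gap days: 74/93 = 79.6%.

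**5. If the SAP 9.1 end date is used in SAP 9.3 and no gap doses are taken.**

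| Capsules by Day 70 | Compliance at I 3 | First gap below 80% |
|---|---|---|
| 73 | 100% | 19 days (73/92 = 79.3%) |
| 70 | 95.9% | 15 days (70/88 = 79.5%) |
| 66 | 90.4% | 10 days (66/83 = 79.5%) |
| 62 | 84.9% | 5 days (62/78 = 79.5%) |

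For a fully compliant patient the threshold is 16 days if I 3 is on Day 60 (63/79 = 79.7%). It is not reached within 20 days if I 3 is on Day 80 (83/103 = 80.6%).

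**6. If the whole I 3 bottle of B capsules counts as taken.** This happens if the bottle is not returned, or if its M 1 return is not credited to Induction. For a patient fully compliant to Day 70, compliance = (73 + B)/(73 + g). B is not given in the documents, so 14 to 35 is an assumed range.
- B = 14: never above 120% (87/74 = 117.6% at g = 1).
- B = 20: above 120% up to g = 4 (93/77 = 120.8%).
- B = 30: 103/74 = 139.2% at g = 1, 103/80 = 128.8% at g = 7, 103/85 = 121.2% at g = 12, then inside the range (103/86 = 119.8%).
- B = 35: above 120% up to g = 16 (108/89 = 121.3%).

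**7. Illustrative effect on PP remission.** Suppose a fraction f of responders is removed in both arms, remitters and other responders alike. PP remission = rem(1 − f)/(1 − resp·f). Inputs are remission 16% vs 6% and active response 60% (Protocol 13.1), and placebo response 32% (Table 5 of that section, which covers total samples of 30 to 150, not Cohort 1). The values of f are assumptions.

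| f | Active | Placebo | Difference |
|---|---|---|---|
| 0 | 16.0% | 6.0% | 10.0 points |
| 5% | 15.67% | 5.79% | 9.9 points |
| 10% | 15.32% | 5.58% | 9.7 points |
| 20% | 14.55% | 5.13% | 9.4 points |

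With Table 5's 57% for active response, the last two differences are 9.7 and 9.3 points.

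**The case against.** The strongest reply is that much of this rests on readings that the SAP does not state.

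- **Idle gap days.** A reader might infer that compliance runs to the day before Maintenance dosing. That end date is written for treatment duration, and SAP 9.3 does not adopt it. On its plain words, a patient who takes nothing after I 3 has a last dose at about I 3, and step 5 falls away. Even on the wider reading, a 19-day gap needs an endoscopy no more than one day before I 3, and no use of the drug supplied for that interval.
- **The M 1 return.** A reader might infer that capsules returned at M 1 are ignored because M 1 is a Maintenance visit. SAP 9.1 treats the supply as extended Induction treatment, Protocol 9.7 collects unused capsules at each visit, and Table 1 reviews compliance at M 1. Crediting the return to Induction is the more natural reading. Step 6 then needs a bottle that never came back.
- **Frequency and status.** Split visits are not the general case, and the PP analyses are sensitivity or additional analyses outside Type I error control.

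All of this stands, and it limits the size of the problem. It does not remove step 4, which uses the narrow reading throughout and still lets doses after I 3 decide membership. Nor is the matter settled elsewhere in the text available: the SAP appendices are not in it, and a definition of last dose date or a cut-off may stand there.

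**Conclusion.** The point holds as a missing cut-off. For patients with split I 3 and M 1 visits, capsules and possibly days after the Week 10 assessment enter the figure that decides PP membership, and this can happen only to Week 10 responders.

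Three stronger conclusions are not supported:
- **That the rule only removes responders.** It can also keep in a patient who was below 80% at I 3.
- **That those affected are exactly the responders in the analysis.** Maintenance entry accepts either Mayo definition, while the PP analyses use the three-component one.
- **That the primary result is biased.** The ITT primary analysis does not use compliance.

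The size cannot be fixed from the documents. It depends on the share of split visits, the I 3 bottle size, whether the M 1 return counts as Induction, and how the last dose date is read. The shift of 0.1 to 0.6 points in the remission difference at 5–20% removal (60% active response) is an illustration without a source for the removal share, and patients kept in are not modelled. The effect is probably small and is confined to the PP sensitivity analysis of remission and the additional PP analysis of response.

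**What to change.** In SAP 9.3 and 5.2, state that compliance for the PP criterion is computed from first dose to I 3 only:
- **Numerator:** capsules dispensed before I 3, minus capsules returned from those bottles.
- **Denominator:** expected capsules up to the last dose from those bottles on or before I 3.
- **Left out:** drug dispensed at I 3, the onsite Maintenance dose, and days from I 3 to M 1.

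Summarise exposure between I 3 and M 1 separately, setting the M 1 return against the I 3 bottle. A patient with 73 of 73 capsules by Day 70 is then 100% compliant whatever happens afterwards, and one with 58 of 73 is excluded whatever happens afterwards.

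The cost is a sentence in each section and a small programming change. No new data are needed, because SAP 9 has the Drug Log recording capsule counts and dates for dispensing and return. This is a cheap improvement.
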